Estimates from the literature were used to calculate the sample size needed for this study for the outcomes of changes from month 0 to month 5 in our primary outcome, heart failure quality-of-life. We assumed that the standard deviations (SD) seen in the current study would be similar to that in a similar study conducted in an urban setting in the United States.¹³ Sample size calculation were based assuming 80% power for a two-sided test at alpha of 0.05, and SD of 20.0. With the outcome of change in heart failure quality of life score from baseline to 5 months, considering as a minimum clinical difference of 10 points in the heart failure quality of life score, the sample size

needed was 63 individuals in each arm. We assumed a retention in the current study of 80%, thus the sample size needed at recruitment was at least 158 (n=79 in each arm)

8) Framework

The superiority hypothesis testing framework will be used, testing whether exposure to the intervention results in better outcomes than exposure to the control standard of care. Comparisons will be presented as differences between arms in changes in outcomes from baseline to 1 month to capture changes in acute heart failure symptoms and 30-day readmission; and from baseline to 5 months of follow-up to capture longer term and potentially sustained benefits.

9) Statistical interim analyses and stopping guidance

- a. Information in interim analyses specifying what interim analyses will be carried out and listing time points
 - i. None planned
- b. Any planned adjustment of the significance level due to interim analysis
 - i. No
- c. Details of guidelines for stopping the trial early
 - i. None

10) Timing of final analyses

Final analyses will begin in Fall 2021 upon completion of all field data collection in Fall 2020 and completion of all medical record data collection (Summer 2021).

11) Timing of outcome assessments

Research staff administered full surveys to both arms at baseline, 1 month, and 5 months. Additional brief surveys were collected at months 2 and 3. Medical record data were collected continuously in both arms from 3 months prior to baseline until 9 months after baseline.

Section 4: Statistical Principles

12) Level of statistical significance

95% confidence intervals and exact p-values (or $p<0.001$) will be reported.

13) Description and rationale for any adjustment for multiplicity and, if so, detailing how the type I error is to be controlled.

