- b. Unable to be contacted: 16 intervention participants were randomized but were not able to be contacted by POH to start the intervention and were considered as early withdrawals. Control participants could not be excluded as "early withdrawals" because the next visit would be a month after the baseline. Therefore, researchers modified the protocol and made a phone call to the control participants, right after the randomization, to simulate the call that the intervention participants had by POH to be enrolled in the food and nutrition program. From among control participants called right after randomization in the modified protocol, 2 could not be reached and were considered early withdrawals.

The number of participants with major and minor protocol deviations will be summarized by study arm.

16) Analysis populations – definition of analysis populations, e.g. intention to treat, per protocol, complete case, safety

- a. Intent to treat - The primary analysis will be intent to treat (ITT). The ITT analysis will include all participants in both arms who were randomized, completed all baseline assessments, and who had at least one follow-up visit. (see CONSORT).
- b. Adjusted intention to treat analysis. To adjust for early withdrawals, a propensity score for receiving the intervention will be developed and used to estimate the probability of each participant to receive the intervention. The adjusted ITT analysis will be performed adjusting for the propensity score and for baseline covariates that were different between arms.
- c. Per protocol - The per protocol analysis will include all participants in the ITT sample with baseline and follow-up evaluations and who adhered to the food and nutrition intervention. The minimal adherence will be considered as receiving at least 50% of weeks food and groceries, and at least 1 visit with the dietitian. This definition may be

revised depending on the distribution of adherence in the intervention participants. See appendix 1 for details about the food and nutrition education intervention.

- d. Complete case— We will not conduct complete case analyses as we will attempt to use all available data from all participants.

Section 5: Trial Population

17) Screening Data –

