- a. **Preliminary/Descriptive analyses.** Frequency tables for all variables and measures of central tendency and variability for continuous variables will characterize the sample and be stratified by randomization arm to check for non-equivalence. If the two arms differ at baseline on any covariates, propensity scores approach will be used to obtain the desired marginal effect estimates under the counterfactual assumption of balanced arm.

25) Analysis methods to be used and how the treatment effects will be presented:

- a. Aim 1, Hypothesis 1. The intervention will lead to improved heart failure quality-of-life (primary outcome) and reduced acute care utilization (secondary outcomes) in the intervention arm compared to the control arm. Intent-to-treat analyses will assess whether the intervention will result in improved changes in primary and secondary outcomes with mixed effects models. These mixed models are equivalent to repeated measures models. Study arm (intervention or control), visits (baseline, month 1 and month 5), and the interactions between arms and visits will be the fixed effects and individuals will be considered as random effects.

Alternative analyses will be done using analysis of covariance in which the 5 month (and 1 month) outcome measures will be regressed on the corresponding baseline outcome measures and study arm. Analysis of covariance allows relaxing the assumption that the

baseline and follow-up measures have a 1:1 relationship and testing the assumption that the relationship between the baseline and follow-up measures are the same.

Additional analyses will be done to check robustness if the two arms differ at baseline by controlling for the propensity score or the covariates that were important in the propensity score.

For primary and secondary outcomes, Box-Cox transformations will be used to correct for skewness if needed.

To compare the probabilities of hospitalization and emergency room visits by study arm, a log-rank test will be performed, and visualized using Kaplan-Meier curves.

- b. Aim 2, Hypothesis, The intervention will improve food security, reduce healthcare utilization, and improve dietary behavior, that in turn will improve mental health (depressive symptoms), and medication adherence. Analysis for intermediate outcomes will be performed using mixed effects models, as described in Aim 1.
- c. Any planned sensitivity analyses for each outcome, where applicable: Not applicable.

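### The primary KCCQ mixed model leaves baseline arm means free, so it estimates a difference in change and forgoes the precision of a baseline-adjusted analysis

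*Combined protocol and SAP*

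**What the plan says.** Section 6, item 25a, assigns the primary and secondary outcomes to a mixed model: "Intent-to-treat analyses will assess whether the intervention will result in improved changes in primary and secondary outcomes with mixed effects models". The model terms are explicit: "Study arm (intervention or control), visits (baseline, month 1 and month 5), and the interactions between arms and visits will be the fixed effects", with a random effect for the individual. Baseline KCCQ is therefore a response, not a covariate, and arm has its own main effect.

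The effect measure agrees. Section 3, item 8, states: "Comparisons will be presented as differences between arms in changes in outcomes from baseline to 1 month", and likewise to 5 months. Item 22a defines the primary outcome as change in KCCQ.

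Item 25a then adds covariance analysis as a secondary route: "Alternative analyses will be done using analysis of covariance in which the 5 month (and 1 month) outcome measures" are regressed on baseline and arm. The SAP's stated reason is that this drops the assumption of a one-to-one relation between baseline and follow-up. Propensity or covariate adjustment is a further check if the arms differ at baseline.

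Section 4, item 16a, makes ITT primary, but its ITT set is limited to randomised participants with complete baseline assessments and some follow-up. Nothing in the SAP sets the two baseline means equal.

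**The concern.** With an arm main effect and an arm-by-visit interaction, the month-5 interaction subtracts each arm's own baseline mean. That fixes the baseline coefficient at about 1, while the best coefficient under equal variances is the correlation. The model also ignores that, among all randomised participants, the true baseline means are equal by design.

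Two things are at stake. The first is precision on the primary outcome: month-5 retention was 60 and 59, below the 63 per arm in item 7, so free precision is worth having. The second is regression to the mean, because an arm that starts higher by chance tends to show less change. The SAP already adjusts its admission and emergency-visit counts for baseline values (item 22b), but not KCCQ in the main model.

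**Working it through.** **Inputs.** Item 7: difference 10, SD 20 for the change score, two-sided alpha 0.05, power 80%. Item 19: 106 and 86 randomised, with 27 and 4 early withdrawals. Item 20: 79 and 82 contacted after randomisation, 75 and 78 at month 1, 60 and 59 at month 5. The correlation ρ is not given; 0.3, 0.5 and 0.7 are assumed. All 192 are assumed to have a baseline KCCQ.

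**The plan's own figure.** n per arm = 2 × 20² × (1.96 + 0.842)² / 10² = 62.8, so 63. Then 63 / 0.8 = 78.75, so 79 per arm and 158 in total. Both figures reproduce.

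**What the planned model estimates.** In 60 simulated complete-data trials (63 per arm, ρ = 0.5), the arm by month-5 coefficient equalled the raw difference in mean change (largest gap 5 × 10⁻¹³). The mean standard error was 3.53, against 3.04 for ANCOVA. The squared ratio is 0.74; theory gives 0.75.

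**Complete data, equal variances.** Var(change) = 2s²(1 − ρ) and Var(ANCOVA) = s²(1 − ρ²), so the ratio is (1 + ρ)/2 = 0.65, 0.75, 0.85. With 63 per arm, power rises from 80.1% to 93.6%, 90.0%, 86.1%.

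**With the reported retention.** Generalised least squares for three visits, equal variances and equal correlations, s chosen so that the change SD is 20. Power = Φ(10/SE − 1.96). The all-randomised set is 106/75/60 and 86/78/59.

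| ρ | SE, free baseline | SE, common baseline | Variance ratio | Power, free | Power, common |
|---|---|---|---|---|---|
| 0.3 | 3.404 | 2.939 | 0.745 | 83.6% | 92.5% |
| 0.5 | 3.456 | 3.136 | 0.824 | 82.5% | 89.0% |
| 0.7 | 3.502 | 3.317 | 0.897 | 81.5% | 85.4% |

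In the 79/82 set the ratios are 0.713, 0.798 and 0.881, with free-baseline power of 81.9%, 81.3% and 80.8%. In the SAP's ITT set (75/78) they are 0.702, 0.790 and 0.875. The common-baseline SE is the same in all three sets: a participant with only a baseline value adds no information on the month-5 contrast once the baseline mean is shared. Widening the set bears on the justification of the constraint, not on precision.

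**Unequal variances.** If the follow-up SD is 1.3 times the baseline SD (an assumption), the 79/82 ratios become 0.847, 0.932 and 0.993. Power moves from 80.3% to 86.4%, 79.7% to 82.4% and 79.5% to 79.8%.

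**Chance imbalance.** A baseline difference d shifts the change estimate by −(1 − ρ)d. For d = 5 points this is 3.5, 2.5 and 1.5 points, against a 10-point target.

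**The mirror case.** If selection into the analysis set creates a true baseline difference d and the arms then change equally, a common-baseline model is off by about (1 − ρ)d. For d = 5 this is the same 3.5, 2.5 and 1.5 points.

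**The case against.** The strongest reply is that nothing here falls short of the plan. Sample size, effect measure and outcome are all expressed as change, and after attrition the planned model still has about 81–84% power under equal variances, against a target of 80%, in a self-described pilot. That stands: a reader might infer an invalid or underpowered test, and the documents do not support it.

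A reader might also infer two unranked analyses and freedom to choose between them. The SAP ranks them: "The primary analysis will be intent to treat (ITT"), the mixed model serves that analysis, and ANCOVA is labelled alternative.

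A third tempting reading is that ANCOVA contradicts item 16d: "We will not conduct complete case analyses as we will attempt to use all available data from all participants". Item 25a does not restrict ANCOVA to completers. Item 24 plans imputation for missed questions and forms, although for missed visits it says only that they are recorded. If ANCOVA were run in the 60 + 59 = 119 completers, little would be lost (88.3% against 89.0% power at ρ = 0.5).

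Nor is the change free of risk. Early withdrawal was 27/106 (25.5%) against 4/86 (4.7%), and the SAP's ITT set also requires follow-up, so equal baseline means are not guaranteed there. Finally, the size of the gain depends on a correlation and variances that the documents do not give. Both objections stand and limit the point; neither removes it.

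**Conclusion.** The point holds as one of efficiency and robustness. The primary model is valid but leaves a baseline measurement underused and exposes the estimate to chance imbalance, which the SAP addresses only through alternative or conditional analyses.

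Under equal visit variances, change SD 20 and ρ of 0.3, 0.5 and 0.7, a common baseline mean lowers the month-5 variance by about 25%, 18% and 10% in the all-randomised set (29%, 20% and 12% in the 79/82 set). The gain shrinks as ρ rises and can be near zero if follow-up scores are also more variable. The calculations use equal correlations and no covariates, so they approximate the model recommended below.

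The equal-baseline constraint is justified by randomisation only in the all-randomised set. In the current ITT set it could bias the estimate by about (1 − ρ) times any selection-induced baseline difference, if the arms would otherwise change in parallel.

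**What to change.** In item 25a, name one primary KCCQ analysis:

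- a mixed model with a common baseline mean (no arm effect at baseline) and an unstructured covariance over baseline, month 1 and month 5;
- fitted to all randomised participants with a baseline KCCQ (up to 106 and 86), not only those with follow-up;
- with the two stratification factors and allocation phase (1:1, then 2:1; item 6) as covariates.

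Keep the free-baseline model and ANCOVA as supportive, and amend item 16a to match. Settle this before KCCQ results by arm are seen, because the analyses can differ in what they estimate as well as in precision.

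The cost is about one paragraph, with the same data and software. The SAP should state the downside: including the early withdrawals makes the constraint correct by design, but their absent follow-up then rests on a missing-at-random assumption, which the wider set does not itself test.

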 1. 16 (15.1%) of randomized intervention and 2 (2.3%) of randomized control participants were unable to be contacted by phone after the baseline evaluations.
 2. 6 (5.7%) participants allocated to the intervention and 2 (2.3%) participants allocated to the control arm were excluded because did not meet eligibility criteria after randomization, and 3 (2.8%) participants in the intervention arm were immediately re-hospitalized.
 3. 1 (0.9%) participant in the intervention arm died after being randomized.
 - ii. Lost to follow up (LTFU) occurred through loss of contact with study participants, moving out of the study area, and death. Intervention participants were also considered LTFU if they withdrew consent. Among

those that were randomized and contacted immediately after randomization (n=79 in intervention arm, and n=82 in control arm):

1. At month 1, 75 (94.9%) of intervention participants and 78 (95.1%) of control participants were retained from month 0.
2. At 5 months of follow-up, 60 (75.9%) of intervention participants and 59 (71.9%) of control participants were retained from month 0.

b. Timing of withdrawal/LTFU data

- i. Intervention participants left the study prior to their first encounter with Project Open Hand were considered withdrawn, otherwise they were considered LTFU.
- ii. Control participants that left the study prior the first call from UCSF staff were considered withdrawn, otherwise they were considered LTFU.
- iii. Participants that were excluded immediately after randomization were also considered early withdrawals.

c. Reasons and details of how withdrawal/LTFU data will be presented

- i. Withdrawal and LTFU data are presented in the CONSORT diagram, stratified by study arm and visit. These data are included to establish lack of bias in screening and retention between the two arms. (See appendix 2)

21) Baseline patient characteristics

We will evaluate several socio-demographic and clinical characteristics at baseline by which we will describe our study sample. These are outlined in Table 1 below and a shell table is provided in the appendix. We will stratify these characteristics by intervention and control arms and report median and the inter-quartile range for continuous variables with skewed data and mean and SD for continuous variables with normal distribution. Categorical variables will be presented as numbers and percentages. No significance testing will be conducted or reported at baseline per CONSORT guidelines.

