Any planned subgroup analyses for each outcome including how subgroups are defined: Additional models and statistical interactions (i.e., product terms) will be performed to identify characteristics of individuals who most benefitted from the intervention, such as biological sex, and food insecurity.

24) Missing data

- a. The study team employed several strategies to account for and address missing data during the CaRDS trial period. To prevent or reduce missing data, data collection was computerized, and the questions were obtained through a trained interviewer. The analyst will examine patterns of non-response and inspect distributions of mediating and outcome variables to identify outlying or unusual values and assess distributional characteristics. Missing data will be categorized into: 1) missed individual questions, 2) missing forms, and 3) missed visits.
- b. Missed individual questions: Multiple imputation will be used to address incomplete data arising from missing forms. The assumption will be that incomplete data arise from a conditionally missing-at random mechanism (MAR). Auxiliary variables will be included to help meet the MAR assumption and sensitivity analyses will be conducted with weighted multiple imputation to assess the MAR assumption. Information on percent of questions missing and imputed will be reported for each variable as appropriate in study manuscripts. Missing items from a scale will be imputing using the other items in the scale.
- c. Missed visits: When a participant missed a visit, either home or clinic or both, this was noted in the study register.

25) Additional analyses – None

26) Harms

i. Data safety:

The study team took several proactive strategies to insure the highest levels of data safety. First, data were collected on password protected tablets or laptops. Data were collected using REDCap and stored on a secure UCSF server. The data was stored in a separate folder than other study materials, and only members of the data team had access to this data. Lastly, any individual who requests study data was required to sign a data agreement which included not sharing the data as well as recommendations for data safety. No identifiers have or will be shared with external investigators.

ii. Details on how adverse events are coded or categorized:

Deaths were reported to UCSF by email within 24 hours after the PIs learned of the occurrence. Other adverse events were not reported.

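### The SAP rules out complete-case analysis but gives no handling for missed visits, so the month-5 ANCOVA defaults to at most 119 completers

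*Combined protocol and SAP*

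**What the plan says.** Four parts of the combined protocol and SAP bear on this.

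- **Primary model (Section 6, item 25 on analysis methods, part a).** A mixed model with participants as random effects: "Study arm (intervention or control), visits (baseline, month 1 and month 5), and the interactions between arms and visits will be the fixed effects". A participant with a month-1 but no month-5 score still contributes.
- **Alternative analysis (same part).** An ANCOVA in which "the 5 month (and 1 month) outcome measures will be regressed on the corresponding baseline outcome measures and study arm". Its rationale begins "Analysis of covariance allows relaxing the assumption that the" and goes on to the one-to-one link between the baseline and later scores. The analysis set is not named.
- **Analysis populations (Section 4, item 16).** The ITT set is those who were "randomized, completed all baseline assessments, and who had at least one follow-up visit". Item 16d adds: "We will not conduct complete case analyses as we will attempt to use all available data from all participants".
- **Missing data (Section 6, item 24).** Three kinds are listed: questions, forms and visits. Under the heading for missed questions, the text reads "Multiple imputation will be used to address incomplete data arising from missing forms", assuming missing at random. Scale items are filled from the rest of the scale. For missed visits, item 24c says only that the absence was recorded.

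On retention, Section 5, item 20 reports 75 intervention and 78 control participants at month 1, and then: "At 5 months of follow-up, 60 (75.9%) of intervention participants and 59 (71.9%) of control participants were retained from month 0".

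**The concern.** A regression of the month-5 score on baseline and arm can use only people who have a month-5 score, unless missed visits are imputed. No section says that they are. The month-5 ANCOVA is then a completer analysis, which item 16d says will not be done.

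The people left out belong to the ITT set as defined, provided that they completed baseline, because one follow-up visit is enough. The mixed model uses their month-1 scores; the ANCOVA discards them. So two things change between the analyses: how baseline enters, and who is in the data. If the two disagree at month 5, the reader cannot tell which change is responsible. The completer ANCOVA also needs a more restrictive missing-data assumption. It adjusts for baseline only, whereas a likelihood analysis can also allow for dropout related to the month-1 score.

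**Working it through.** **1. The plan's own sample size.** Inputs from item 7: difference 10, SD 20, two-sided alpha 0.05, power 80%, retention 80%.

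n per arm = 2 × (1.960 + 0.842)² × 20² / 10² = 62.8, so 63. Then 63 / 0.80 = 78.75, so 79 per arm and 158 in total. Both stated figures reproduce. With 60 and 59 at month 5, power by the same method is 77.8%, against 80.1% at 63 per arm.

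**2. Who is left out at month 5.** Counts from item 20.

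- Seen at month 1: 75 + 78 = 153. Seen at month 5: 60 + 59 = 119.
- Intervention: 75 − 60 = 15 (20.0%). Control: 78 − 59 = 19 (24.4%). Total 34 of 153 (22.2%).
- This assumes that everyone seen at month 5 was also seen at month 1. In each arm 4 people missed month 1 (79 − 75 and 82 − 78). If all 8 returned at month 5, the number left out is 34 + 8 = 42. The range is 34 to 42.
- It also assumes that a retained participant has a KCCQ score.

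**3. How much it could matter.** The documents give neither the correlations between visits nor the dropout mechanism, so both are assumed. The simulations set the true effect to zero, start from 75 and 78 people at month 1, and lose about 20% and 24% by month 5. Where dropout depends on month 1, its odds rise by e¹ = 2.7 per SD lower score. Set A has equal correlations of 0.3, 0.5 or 0.7 and an SD of change of 20 (3000 runs each). Set B has an SD of 20 at each visit and correlations of 0.4–0.5 (baseline, month 1), 0.3–0.4 (baseline, month 5) and 0.6–0.7 (months 1, 5), with 2500 runs each.

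| Dropout after month 1 | ANCOVA bias, set A | ANCOVA bias, set B |
|---|---|---|
| Random | −0.02 to 0.02 | about 0 |
| Same dependence on month 1 in both arms | −0.16 to −0.19 | 0.3 to 0.5 in size |
| Dependence in control arm only | −0.86, −1.15, −1.24 | −1.87, −2.10, −2.92 |
| Opposite directions by arm | −1.61, −2.24, −2.70 | not run |

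A negative sign is against the intervention. It reverses if the arms swap.

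The sets differ because the bias scales with the slope of month 5 on month 1 given baseline, (r15 − r01·r05)/(1 − r01²). In set A this is ρ/(1 + ρ), from 0.3/1.3 = 0.23 to 0.7/1.7 = 0.41. In set B, with 0.4, 0.3 and 0.6, it is (0.6 − 0.12)/(1 − 0.16) = 0.57. Repeat runs in the set B range gave 1.7 to 2.8 points for the control-only case, and 0.9 to 1.5 with half the log-odds slope.

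A likelihood estimate with unstructured covariance that uses month 1 stayed within about 0.15 points in both sets. Under random dropout in set B its standard error was 3.23 against 3.31, 3.45 against 3.60, and 3.31 against 3.54, which is 2% to 6% smaller.

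**4. Against the SAP's own primary model.** If the participant random effects are read as a random intercept, the primary model is itself biased by about 0.5 to 1.3 points in the control-only case. The gap between the two planned analyses is then about 1.2 to 1.6 points, with standard errors of roughly 3.4 to 4.1.

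**The case against.** The strongest reply is that the SAP never says the ANCOVA is run on completers. Item 24b plans imputation with auxiliary variables, its scope is loosely worded, and a missed visit also leaves a missing form. If the imputation reached month-5 scores, nobody in the ITT set would be dropped. This stands to the extent that the analysis set is unspecified rather than declared to be completers. But item 24 lists missed visits as a separate class and gives that class no method, so the default is as described.

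Second, the ANCOVA is offered to relax an assumption about baseline, not to test missing data. That is correct, and changing the sample at the same time blurs exactly that comparison.

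Third, the larger biases need month-1-related dropout that differs by arm. The documents do not show this, and the arms lost similar shares after month 1 (20.0% and 24.4%). That also stands. Early withdrawal was uneven (27 against 4), and controls were due their meals only from the sixth month. Differential dropout is therefore possible, but it is not established.

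A reader might also infer that the ANCOVA is the only check on the primary result. It is not. Although the plan states "Any planned sensitivity analyses for each outcome, where applicable: Not applicable", items 16, 24 and 25 provide for a propensity-adjusted ITT analysis, a per-protocol analysis, robustness checks if the arms differ at baseline, and weighted multiple imputation to examine the missing-at-random assumption.

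**Conclusion.** The concern holds in a limited form. Items 16d, 24c and 25a are not reconciled, and as written the month-5 ANCOVA leaves out 34 to 42 people who have a month-1 visit. The month-1 ANCOVA keeps them.

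The possible bias is about zero under random dropout, under about 0.5 points with the same mechanism in both arms, and about 1 to 3 points with dependence in one arm. The last is 10% to 30% of the 10-point planning difference and less than one standard error of the estimate. These sizes rest on assumed correlations and dropout odds, not on trial data.

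A reader might infer that the primary result is compromised, or that the ANCOVA is useless as an alternative. The documents support neither: the primary model uses the month-1 scores, and the ANCOVA is one of several secondary checks.

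**What to change.** Either of two changes would do.

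- **Longitudinal ANCOVA.** Fit one model with months 1 and 5 as joint responses, baseline-by-visit and arm-by-visit terms, and read both arm effects from it. Use the same covariance structure here and in the primary model, preferably unstructured in both. Changing the covariance in one model only would add a second difference and defeat the purpose.
- **Imputation.** Keep the month-5 ANCOVA, but run it on data multiply imputed for missed visits with month-1 scores in the imputation model.

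State the ANCOVA's analysis set, and amend items 16d and 24c to match the choice. If a completer ANCOVA is still wanted, label it as such and also fit the mixed model in the same people, so that the two can be compared.

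The cost is SAP wording and slightly more modelling, with no new data. Both options rely on dropout being random given baseline and month 1. The gain in precision is small.
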